3.5.2. Medical History

Medical history in addition to COVID-19 disease history and demographics will be collected at screening. Smoking status will be collected. Medication history of prescription or nonprescription drugs (including vaccinations), and dietary and herbal supplements taken within 30 days prior to the planned first dose will be collected. All doses of COVID-19 vaccinations administered at any time before study participation will be collected and summarized.

3.5.3. Height and Weight

Height and weight will be measured and recorded at screening.

3.5.4. Laboratory Data

The [Appendix 3](#) lists clinical safety laboratory tests to be performed and the protocol SoA for the timing and frequency.

3.5.5. Vital Signs

Vital signs measure include temperature, pulse rate, respiratory rate, oxygen saturation level, and blood pressure.

4. ANALYSIS SETS (POPULATIONS FOR ANALYSIS)

Data for all participants will be assessed to determine if participants meet the criteria for inclusion in each analysis population.

Participant Analysis Set	Description
Enrolled	"Enrolled" means a participant's, or their legally authorized representative's, agreement to participate in a clinical study following completion of the informed consent process and assignment to study intervention. A participant will be considered enrolled if the informed consent is not withdrawn prior to participating in any study activity after screening. Potential participants who are screened for the purpose of determining eligibility for the study, but do not participate in the study, are not considered enrolled, unless otherwise specified by the protocol.
SAS	All participants assigned to study intervention and who take at least 1 dose of study intervention. Participants will be analyzed according to the product they actually received.

Defined Analysis Set	Description
PK Concentration	The PK concentration population is defined as all participants assigned to investigational product and treated who have at least 1 concentration measured.
PK Parameter	The PK parameter analysis population is defined as all participants assigned to investigational product and treated who have at least 1 of the PK parameters of interest measured.

5. GENERAL METHODOLOGY AND CONVENTIONS

5.1. Hypotheses and Decision Rules

This is single arm study and has no statistical hypotheses tested and no formal decision rules for interpreting the study results. All analyses will be descriptive.

5.2. General Methods

Descriptive statistics for all endpoints will be provided by cohort and time point. For most summary tables, unless stated otherwise, cohorts will be presented both separately and combined.

5.2.1. Analyses for Binary Endpoints

For binary endpoints, number and proportion of participants with the event of interest (with corresponding sample size) will be summarized for each cohort and overall.

5.2.2. Analyses for Continuous Endpoints

For continuous endpoints, values and/or changes from baseline over time, as applicable, will be summarized for each cohort and overall. Standard descriptive statistics (n, mean, standard deviation, median, interquartile range, minimum, and maximum) will be utilized.

5.2.3. Analyses for Categorical Endpoints

For categorical endpoints, number and proportion of participants for each category (with corresponding sample size) will be summarized for each cohort and overall.

5.3. Methods to Manage Missing Data and Non-Quantifiable Data

In summary tables of concentration data by cohort, visit day and time, statistics will be calculated having set concentrations to missing if one of the following applies:

- A concentration has been collected as ND (not done) or NS (no sample), or
- A deviation in sampling time is of sufficient concern or a concentration has been flagged anomalous by the pharmacokineticist. In such cases, data for all participants will be assessed to determine if samples meet the criteria for exclusion from analysis prior to releasing the database, and classifications will be documented per standard operating procedures.

SARS-CoV-2 RNA < LLOQ is imputed as $1.7 = \log_{10}(50)$ for non-missing results.

As all analyses are descriptive, missing endpoint data will result in a summary where the N for that endpoint (and time point) is smaller than the total N of the corresponding analysis set. No imputation of the missing data will be performed.

Missing PK concentration values will generally be handled as described above. Non-missing concentrations that are below the limit of quantitation will be reported as such in listings and imputed as zero for summary tables and figures.

Additional details for handling missing data in the population PK modeling will be described in a population modeling analysis plan.

Missing safety data such as dates or severities of adverse events will be handled using standard algorithms in accordance with CDISC and CaPS standards.

6. ANALYSES AND SUMMARIES

6.1. Primary Endpoint

6.1.1. Primary Endpoint/Estimand Analysis

6.1.1.1. Main Analysis

Incidence of TEAEs through Day 34, SAEs, and AEs leading to discontinuation will be summarized with number and percent of participants in the SAS for each cohort, and overall, in accordance with CDISC and CaPS standards.

6.1.1.2. Sensitivity/Supplementary Analysis

Not applicable.

6.2. Secondary Endpoint(s)

6.2.1. Plasma nirmatrelvir PK parameters: CL/F, V_z/F, AUC_{0-tau}, C_{max}, t_{1/2} and C_{trough}

- Nonlinear mixed effect modeling will be performed using the PK concentration analysis set (see Section 4) to evaluate pharmacokinetic parameters of nirmatrelvir (CL/F, V_z/F, AUC_{0-tau}, C_{max}, t_{1/2} and C_{trough}). The detailed procedures for the population PK analysis, including the model implementation and evaluation will be described in a population modeling analysis plan. Also, the results of the analysis will be summarized in a population modeling and analysis report, separate from the clinical study report.
- Plasma concentrations of nirmatrelvir from venous or Tasso samples will be summarized using the PK concentration analysis set. A listing of plasma concentrations at the nominal sampling time by participant, method of blood collection, and cohort will be provided. A listing of deviations from the nominal sampling time will also be provided. For each cohort, and overall, the plasma concentrations will be summarized by nominal sampling time using appropriate descriptive statistics (eg, number of participants/samples, number of concentrations at or above the lower limit of quantification (NALQ), mean, SD, minimum, median, maximum, and coefficient of variation).
- Individual nirmatrelvir plasma concentration profiles (ie, concentration vs. time data) will be presented graphically by cohort (ie, spaghetti plots) using actual sample collection time on both linear and semilogarithmic scales. Median concentration time profiles will be presented by cohort on both linear and semilogarithmic scales using nominal sampling time. Additional graphical presentations of PK data may be included at the discretion of the PK scientist.

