**PK SAMPLING SCHEMA 2 – COHORT 2: HD cohort with 1st Dose on HD day that is Monday**

Study Day	Day 1 – HD MONDAY	Day 2 – no HD TUESDAY	Day 3 – HD WEDNESDAY	Day 4 – no HD THURSDAY				Day 5 – HD FRIDAY
PF-07321332 (nirmatrelvir)/ritonavir administration	X b	X	X b		X			X b
Hours after dosea	1 – 3		Before and During HD	0	0.5 – 3	4 – 8	9 – 15	Before HD start
PK blood sampling (Tasso)	X f		X c	X c	X f	X f	X f	[X c ]
PK blood sampling during HD (arterial and venous ports)			X d					X e
Hematology blood sample (hematocrit)			X i					
Blood:Plasma Ratio sample (venous)	X h		X g, h		X h			[X g, h ]

- a. Hours are in reference to the QD dose of PF-07321332 (nirmatrelvir)/ritonavir on each study day. The Day 1 dose should be taken at the clinic visit.
- b. On dialysis days, participants will take study intervention as soon as feasible after HD.
- c. Tasso blood sample: Tasso device placed by participant, caregiver, home health provider, or other healthcare provider (as appropriate).
- d. Venous blood samples: HD staff to obtain PK blood samples from the HD filter arterial port and the venous port at 0 hr (prior to start of HD) and at 0.5, 1, 2, 3, and 4 hours post start of dialysis.
- e. Day 5 PK blood sample: If participant goes to HD treatment prior to going to investigational site on Day 5, then HD staff to obtain this venous sample prior to the start of dialysis from the venous HD line. If participant goes to investigational site prior to going to HD on Day 5, then investigational site staff can obtain PK sample using the Tasso device.
- f. Tasso blood samples: After dosing study drug, Tasso device placed by participant, caregiver, home health provider, or other healthcare provider (as appropriate). Collect the consecutive PK samples within the prescribed windows with each sample taken a minimum of 2 hours apart.
- g. Blood:Plasma Ratio venous sample: Collect at 0 hr prior to start of HD.

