**PK SAMPLING SCHEMA 6 - COHORT 2: HD cohort with 1st Dose on HD day that is Friday**

Study Day	Day 1 – HD FRIDAY	Day 2 - no HD SATURDAY	Day 3 - no HD SUNDAY				Day 4 - HD MONDAY	Day 5 - no HD TUESDAY
PF-07321332 (nirmatrelvir)/ritonavir administration	X b	X		X			X b	X c
Hours after dosea	1 - 3		0	0.5 - 3	4 - 8	9-15	Before and During HD	0
PK blood sampling (Tasso)	X e		X d	X e	X e	X e	X d	X d
PK blood sampling during HD (arterial and venous ports)							X f	
Hematology blood sample (hematocrit)							X i	
Blood:Plasma Ratio sample (venous)	X h		[X h ]				X g, h	[X h ]

- a. Hours are in reference to the dose of PF-07321332 (nirmatrelvir)/ritonavir on each study day. The Day 1 dose should be taken at the clinic visit.
- b. On dialysis days, participants should take the dose of study intervention as soon as feasible after HD.
- c. For the Day 5 in-person visit, 1) if the time of the scheduled visit is within the dosing window ( $\pm$  4 hours), participants should wait to take the dose of PF-07321332 (nirmatrelvir)/ritonavir until the in-person visit. The dose will be taken after the pre-dose PK sample has been obtained; 2). If the time of the scheduled visit is not within the dosing window ( $\pm$  4 hours), participants should take the dose of PF-07321332 (nirmatrelvir)/ritonavir at the participant's usual time and PK samples taken per the schedule.
- d. Tasso blood sample: Tasso device placed by participant, caregiver, home health provider, or other healthcare provider (as appropriate).
- e. Tasso blood samples: After dosing study drug, Tasso device placed by participant, caregiver, home health provider, or other healthcare provider (as appropriate). Collect the consecutive PK samples within the prescribed windows and with each sample a minimum of 2 hours apart.
- f. Venous blood samples: HD staff to obtain PK blood samples from the HD filter arterial port and venous port at 0 hr (prior to start of HD) and at 0.5, 1, 2, 3, and 4 hours post start of dialysis.
- g. Blood:Plasma Ratio venous sample: Collected at 0 hr prior to start of HD

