For PK assessments in severe renal impairment participants on HD, samples will be collected on Days 1 through 5 of dosing with respect to the participant's dialysis sessions during treatment. If at home, this should be collected using a Tasso device or may be done at an in-person visit, unless otherwise specified in the [SoA](#). During HD, venous port (entering dialyzer) and arterial port (exiting the dialyzer) blood samples will be collected at 0, 0.5, 1, 2, 3 and 4 hours post the start of dialysis.

This study will use the program-level E-DMC. The E-DMC is independent of the study team and includes only external members. The E-DMC charter describes the role of the E-DMC in more detail for this study.

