### **8.1.1. Tasso sample training and collection**

Participants (and/or caregivers) completing Tasso M20 device training will use the Tasso M20 device at home to collect PK samples during the times specified in the [PK schema](#). Samples collected at the site that are not specified to be arterial port or venous port samples for HD participants (Cohort 2) will also be simultaneously collected by site staff using the Tasso device and venous sample blood draw. At Screening (or during the Screening Period) participants and/or caregivers will be instructed on administration of the Tasso M20 device and will demonstrate their understanding by self-collecting or a caregiver collecting a sample on site using this device. This sample is for training purposes and no testing will be performed on it. Participants unwilling or unable to complete Tasso training and applied demonstration of the tool, may utilize support from a caregiver to administer the Tasso device. If the site finds the participant (or caregiver) is willing and able to correctly administer the device, the participant will enter the study and go home with sufficient quantities of the Tasso device as well as all required study materials per protocol. The site will document participant's and/or caregiver's training in source and confirm the participant has continued the required Tasso sample collection on Day 2 at home via a telehealth visit. Additional site support and training may be required for participants.

If a participant (or caregiver) is unwilling or cannot demonstrate proficiency collecting the sample using the Tasso device, then the site must document the participant as a screen failure based on the inclusion criteria in Section [5](#) unless the participant has the option to use a home healthcare provider as described in Section [8.1.4](#).

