### 8.5.2. Hemodialysis

Participants assigned to Cohort 2 will begin study intervention either on a HD treatment day or non-HD treatment day. The day of the participant's first IP dose, either on an HD day or on a non-HD day (ie, Treatment Day 1) will determine the subsequent PK sample schedule as described in the [PK Sampling Schema](#).

Participants beginning IP administration on an HD treatment day (ie, Treatment Day 1) will have PK samples collected per the [PK Sampling schema](#) in Section 1.3 including samples drawn from HD lines before and during HD treatment days. Obtain blood samples for **hematology (hematocrit)** at time 0 (venous port sample) and time of the last PK draw (venous port sample) on dialysis, to be used for dialysis clearance (CLd) calculations. Time 0 is defined as the time period prior to the start of the HD blood pump.

If the participant is assigned to begin IP treatment (ie, Treatment Day 1) on a non-HD day, the participant will have samples collected per the [PK Sampling Schema](#) in Section 1.3. Obtain blood samples for hematology (hematocrit) at time 0 (venous port sample) and time of the last PK draw (venous port sample) on dialysis, to be used for dialysis clearance (CLd) calculations. Time 0 is defined as the time period prior to the start of the HD blood pump.

Additional details regarding the HD treatment will be captured in the database (refer to CRF completion guidelines).

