6.2.2. HD clearance (CL_d) of PF-07321332 (nirmatrelvir)

Hemodialysis clearance (CL_d) of nirmatrelvir will be calculated using the following relationship:

$$CL_d = [(C_{in} - C_{out}) / C_{in}] \times [Q_b \times (1 - HCT)]$$

where C_{in} and C_{out} are plasma concentrations measured in blood samples entering and exiting the dialyzer, respectively; Q_b and HCT are blood flow rate entering the dialyzer and hematocrit measured at each collection time, respectively. Individual time point CL_d values obtained using this method will be used to calculate an average subject CL_d.

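### Could samples leaving the dialyzer be pooled with samples entering it in the by-time plasma summaries of SAP 6.2.1?

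*SAP*

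**What the plan says.** SAP 6.2.1: "Plasma concentrations of nirmatrelvir from venous or Tasso samples will be summarized using the PK concentration analysis set". The tables are by nominal time, for each cohort and overall. Individual and median profiles are plotted by cohort. SAP Appendix 1 repeats this and shows the collection method only in the listing.

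The protocol describes port sampling during hemodialysis (HD) in three ways:

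- Section 1.3, PK Sampling Schema 2, footnote d: "Venous blood samples: HD staff to obtain PK blood samples from the HD filter arterial port and the venous port at 0 hr". Schema 6, footnote f, has the same heading.
- Section 8.1.1 applies to "Samples collected at the site that are not specified to be arterial port or venous port samples for HD participants (Cohort 2"), which "will also be simultaneously collected by site staff using the Tasso device and venous sample blood draw". Here port samples are set apart from venous draws.
- Section 4.1: "venous port (entering dialyzer) and arterial port (exiting the dialyzer) blood samples will be collected at 0, 0.5, 1, 2, 3 and 4 hours". Here the venous port is the entering side only.

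For dialysis clearance, SAP 6.2.2 defines its two concentration terms as "plasma concentrations measured in blood samples entering and exiting the dialyzer". Protocol 8.5.2 adds: "Time 0 is defined as the time period prior to the start of the HD blood pump".

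**The concern.** A value measured after the dialyzer has had drug removed from it, so it is not a systemic concentration. If the word venous in SAP 6.2.1 takes its meaning from the schema footnotes, values from both sides of the dialyzer qualify for the same table row and the same profile. The Cohort 2 mean and median during HD would then be too low, the spread too wide, and an individual plot would carry two values at one time. The sample count in the table would show extra records but not that half of them came from the exit side. Paired Tasso and venous samples could also be counted twice at one nominal time. Two programmers working from the same sentence could produce different Cohort 2 tables.

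**Working it through.** **1. Does any visible rule remove a correctly drawn exit sample?** No.

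- SAP Section 4 defines the PK concentration set by participant, so it selects no samples.
- SAP 5.3 sets to missing only samples not done or not taken, those with a worrying time deviation, and those flagged as anomalous.
- SAP Appendix 2.3 covers protocol deviations only.
- Protocol 9.3.3, where visible, adds no exclusion.

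**2. What could venous cover?**

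| Reading | Source | Port values admitted during HD |
|---|---|---|
| A | Schema footnotes | Both sides, pooled |
| B | Protocol 8.1.1 | None |
| C | Protocol 4.1 | Entering side only |

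Only reading A mixes the two sides.

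**3. Which reading fits the SAP sentence?**

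- SAP 6.2.1 sets venous against Tasso. Protocol 8.5.3 makes the same contrast between collection methods: Tasso is used, and a venous draw replaces it if the device fails.
- Each HD schema gives port sampling its own row, separate from the Tasso row and the blood-to-plasma ratio row.
- The schema hours run from the dose. The port draws are timed from the start of dialysis, under a column that carries no post-dose hour, and on HD days the dose comes after dialysis. No document says that 0.5 to 4 h of HD are rows of the by-time table.
- SAP 6.2.2 gives entering and exiting values their own analysis, identified by direction.

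All four points tell against reading A.

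**4. Size if reading A were nevertheless applied.** The plan states no figure to reproduce. Let E = (Cin − Cout)/Cin. The documents give no E, so 0.2, 0.5 and 0.8 are assumptions. With equal numbers from each side:

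- Pooled mean = (Cin + Cout)/2 = Cin × (1 − E/2).
- Pooled median, for lognormal values and a common E, = entering median × √(1 − E). On the log scale the two halves are symmetric distributions log(1 − E) apart, so the median is midway.
- Pooled CV = √{[(1 + cv²)(1 + (1 − E)²)/2]/(1 − E/2)² − 1}. With cv = 0.4, the largest planning value in SAP 2.4, and E = 0.5: √(0.725/0.5625 − 1) = √0.289 = 0.54.

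| Assumed E | Mean | Median | CV, from 0.40 |
|---|---|---|---|
| 0.2 | −10% | −11% | 0.42 |
| 0.5 | −25% | −29% | 0.54 |
| 0.8 | −40% | −55% | 0.82 |

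Port samples per session: 6 times × 2 ports = 12. Of these, 5 are exit samples after the start of HD, or 5 × 12 = 60 over 12 participants. They would not share one row per time, because SAP 5.3 tabulates by visit day and port sampling falls on Day 3 (Schemas 2 to 5), Day 4 (Schemas 6 to 10) or Day 5 (Schemas 11 and 12).

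**5. Duplicates.** At 0 h on the sampled HD day there can be 3 or 4 records per participant: Tasso, two ports and, if drawn separately, ratio plasma. The blood pump has not started, so this is repeat counting without extraction bias. A total over the whole schedule is not firm. In Schemas 2 and 3 the Day 4 ratio cell has no brackets although footnote h makes it a replacement sample, and the Day 5 Tasso cell is bracketed although footnote e allows an HD-line draw instead. The total depends on how those cells are read.

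**The case for a change.** The strongest case for a change is that a SAP should not leave the meaning of a summary to the analyst's good sense. No visible text names the dialyzer side, the protocol uses venous inconsistently, and flagging a valid exit sample as anomalous would stretch that flag beyond its purpose. The whole study is descriptive, so calling these tables merely descriptive does not make them unimportant. They are the concentration results reported under this SAP, while the model results go to a separate report, and the effect of HD on PK is a secondary objective. The planned median profile would move more than the mean.

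The inconsistency in wording stands, and so does the absence of a visible rule. It does not follow that pooling is likely. It would require carrying a footnote heading into an SAP sentence about collection methods, adding table rows on a clock that the schemas do not use for post-dose times, and overlooking that the next SAP subsection separates the two sides. SAP Appendix 2.2 sends derivations to an Analysis and Reporting Plan that is not available here, and parts of the SAP and of protocol 9.3.3 are redacted, so a selection rule may exist. The listing shows collection method and actual time, which would help a reader trace an odd row. One value per participant per time is a convention, and the SAP openly allows for more samples than participants.

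**Conclusion.** No change to the plan. This is a record-selection detail for descriptive tables and plots that a pharmacokineticist would be expected to fill by keeping exit-side values for the clearance calculation. The fall of 10% to 40% in the mean applies only if the least natural of the three readings is used, only at the five times after HD starts, and only for the assumed E of 0.2 to 0.8. At 0 h the issue is repeat counting alone.

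The primary endpoint is safety, no hypothesis is tested and no decision rule uses these tables. Dialysis clearance needs both sides and names them by direction. Whether the population PK model is affected cannot be judged, because its data handling is in a separate plan. The conclusion assumes that the analysts treat port samples as SAP 6.2.2 does; nothing in the documents suggests otherwise.

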6.2.2. HD clearance (CL_d) of PF-07321332 (nirmatrelvir)

Hemodialysis clearance (CL_d) of nirmatrelvir will be calculated using the following relationship:

$$CL_d = [(C_{in} - C_{out}) / C_{in}] \times [Q_b \times (1 - HCT)]$$

where C_{in} and C_{out} are plasma concentrations measured in blood samples entering and exiting the dialyzer, respectively; Q_b and HCT are blood flow rate entering the dialyzer and hematocrit measured at each collection time, respectively. Individual time point CL_d values obtained using this method will be used to calculate an average subject CL_d.

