Type of Visit	In-Person Site or Home Health Visit with Telehealth	In-Person Site Visit	In-Person Site or Home Health Visit	Telehealth Visit	In-Person Site, Home Health or Telehealth Visit	Telehealth Visit	In-Person Site, Home Health or Telehealth Visit	In-Person Site, Home Health or Telehealth Visit	
Weight, height	X		X						
 
Height may be self-reported.
 
HD treatment days will require database entry of pre- and post-dialysis weight. See Section 8.3.2.
 

LABORATORY									
Hematology	[X]	X	X		[X]		[X]	[X]	
 
Screening visit: Laboratory assessments are not required at screening unless deemed necessary by the investigator to confirm eligibility. The medical laboratory test abnormalities within 3 months prior to screening must be closely assessed.
 
Screening visit: If Laboratory assessments cannot be verified within 3 months of screening, local laboratory testing should be performed at screening to confirm eligibility for the study.
 
Baseline laboratory assessments should be collected prior to first dose of study intervention.
 
SARS-CoV-2 serology sample should be collected if an in-person (in clinic or home health) visit is conducted at Day 14±2, Day 34±3 or ET visits.
 
Safety laboratory tests (hematology, blood chemistry) at Days 14±2 and 34±3/ET are required only if clinically significant abnormal laboratory values were present from a sample drawn at the previous study visit when laboratory assessments were performed.
 
Abnormal laboratory values related to AEs should be followed until resolution. See Section 8.3.4 and Appendix 2.
 

Blood chemistry	[X]	X	X		[X]		[X]	[X]	
SARS-CoV-2 Serology (IgG and IgM)	[X]	X	X		[X]		[X]	[X]	

PFIZER CONFIDENTIAL

Visit Identifier	Screening	Baseline (Day 1)	Day 5	Day 10	Day 14	Day 21	Day 34	ET	Notes
Visit Window	Day -1 to Day 1	0 days	0 days	±1 day	±2 days	±2 days	±3 days		
Type of Visit	In-Person Site or Home Health Visit with Telehealth	In-Person Site Visit	In-Person Site or Home Health Visit	Telehealth Visit	In-Person Site, Home Health or Telehealth Visit	Telehealth Visit	In-Person Site, Home Health or Telehealth Visit	In-Person Site, Home Health or Telehealth Visit	

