Participant-completed electronic diary (study intervention log)		Day 1 through Day 5							
 
The electronic diary will be provided or application downloaded to participant's own device and training completed at the Baseline visit.
 
Daily dosing will be entered in an electronic diary Days 1 through Day 5. The Day 1 dose at the site should be entered in the eDiary by the participant (or caregiver) while on site.
 
For participants who are using an eDiary provided through the study, the eDiary will be collected on Day 5, the next scheduled visit or ET visit after completion of dosing log entries on the device.
 

PFIZER CONFIDENTIAL

Visit Identifier	Screening	Baseline (Day 1)	Day 5	Day 10	Day 14	Day 21	Day 34	ET	Notes
Visit Window	Day -1 to Day 1	0 days	0 days	±1 day	±2 days	±2 days	±3 days		
Type of Visit	In-Person Site or Home Health Visit with Telehealth	In-Person Site Visit	In-Person Site or Home Health Visit	Telehealth Visit	In-Person Site, Home Health or Telehealth Visit	Telehealth Visit	In-Person Site, Home Health or Telehealth Visit	In-Person Site, Home Health or Telehealth Visit	
Investigational Site check of participant eDiary dosing entries		Day 1 through Day 5							
 
On Days 1-5, site personnel will review eDiary participant dosing entries daily on the Trial Manager portal and contact participant if not completed.
 
See Section 6.5.
 

Record HD Details (Cohort 2 only)		HD Days during Day 1 through Day 5							
 
During HD treatment, site staff should record relevant HD details on the designated CRF.
 

Retrieval of unused study intervention and empty study intervention containers			X		[X]			[X]	
 
If the Day 5 visit is conducted prior to last dose of study intervention on Day 5, empty study intervention containers, and unused study intervention should be returned at the next in-person visit (Day 14). The electronic diary should be reviewed and device should be returned if applicable.
 
See Section 6.5.
 

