- h. Blood:Plasma Ratio venous sample: Collect immediately before or after a Tasso sample but no longer than 15 minutes between the samples. The blood:plasma ratio sample tube is divided into 1 blood sample (in a cryovial) and, after centrifugation, 1 plasma sample (in another cryovial) (reference the Central Lab Manual). Collect blood:plasma ratio samples on Day 1 and Day 3. If one sample is missed, it may be collected on Day 4 or Day 5. Always collect a corresponding Tasso sample for each blood:plasma ratio sample.
- i. Hematocrit: Obtain 2 hematology blood samples (hematocrit) - one at time 0 hr (venous port sample) and one time of the last PK draw (venous port sample) during HD (hematocrit needed for CLd calculations).

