### **8.3.2. Height and Weight**

Height and weight will be measured and recorded as source data at screening. Height may be self-reported.

On HD treatment days, record the pre- and post- dialysis weight on the appropriate CRF. Refer to CRF completion guidelines.

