6.2.3. Fraction of PF-07321332 (nirmatrelvir) dose removed from the body by dialysis (F_d)

Fraction of nirmatrelvir dose removed from the body by dialysis (F_d) will be calculated as follow:

[figure not shown]
$$F_d = 100\% \times A_d / Dose$$

where A_d is the amount of drug removed by the dialysis and is calculated as follows:

[figure not shown]
$$A_d = CL_d \times AUC_{t_0-t_1}$$

where for $AUC_{t_0-t_1}$, t_0 marks the start time and t_1 the termination of the hemodialysis session.

CCI

CCI

CCI

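### The SAP's hemodialysis clearance formula omits drug carried off with ultrafiltrate, so CLd, Ad and Fd are understated when net fluid is removed, by an amount the documents do not fix

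*SAP*

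**What the plan says.** SAP 6.2.2 sets CLd = [(Cin − Cout)/Cin] × Qb × (1 − HCT), where Cin and Cout are plasma concentrations entering and leaving the dialyzer. It states that "Q_b and HCT are blood flow rate entering the dialyzer and hematocrit measured at each collection time, respectively". CLd is calculated at each time point and then averaged within participant.

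SAP 6.2.3 sets Ad = CLd × AUC over the session and Fd = 100% × Ad/Dose. The quantity is described as total removal: "Fraction of nirmatrelvir dose removed from the body by dialysis (F_d) will be calculated as follow". CLd and Fd are the endpoints for the secondary objective on the effect of HD (Protocol Section 3).

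On data, Protocol 8.3.2 says "On HD treatment days, record the pre- and post- dialysis weight on the appropriate CRF", and the Schedule of Activities repeats the requirement. The same schedule says "During HD treatment, site staff should record relevant HD details on the designated CRF", without listing the items. On hematocrit, PK Sampling Schema 2, footnote i, says "Obtain 2 hematology blood samples (hematocrit) - one at time 0 hr (venous port sample) and one time of the last PK draw"; the other Cohort 2 schemas and Protocol 8.5.2 agree.

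**The concern.** Applying inlet plasma flow to both concentrations is right only if as much plasma water leaves the dialyzer as enters it. Fluid removal breaks that condition: drug also leaves in the ultrafiltrate, and the formula gives it no credit. The visible SAP has no ultrafiltration term and does not say that convective removal is excluded by design.

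The omission matters most where extraction is low, because the missing term is then large relative to the counted one. In the limiting case where Cout equals Cin, the SAP formula returns zero clearance although drug leaves at rate Quf × Cin. Protocol Section 1.1 (Ethical Considerations) notes that nirmatrelvir PK had not been evaluated in HD patients, so the extraction that applies is not known in advance.

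A second, separate gap is that the formula needs hematocrit at times when the protocol does not measure it.

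**Working it through.** The documents state no value of CLd, Ad or Fd, so there is no planned figure to reproduce.

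**Mass balance.** Write Qp = Qb(1 − HCT) for inlet plasma flow and E = (Cin − Cout)/Cin for extraction.

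- Removal rate = Qp × Cin − (Qp − Quf) × Cout = Qp(Cin − Cout) + Quf × Cout.
- Dividing by Cin: CLd(total) = Qp × E + Quf × (1 − E).
- The SAP formula is the first term only.
- Relative shortfall = Quf(1 − E) / [Qp × E + Quf(1 − E)].

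The omitted term is positive whenever Quf > 0 and Cout > 0. For a given AUC, Ad and Fd carry the same percentage, since both are proportional to CLd.

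**Size, on assumed inputs.** Neither document gives blood flow, hematocrit, extraction or fluid volume. Assume Qb = 300 mL/min and HCT = 0.35, so Qp = 300 × 0.65 = 195 mL/min. Assume 1–4 L removed over 4 h (240 min), so Quf = 4.2–16.7 mL/min. The 4 h span matches the port sampling window in Protocol 4.1.

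| E | SAP CLd (mL/min) | Omitted term (mL/min) | Shortfall |
|---|---|---|---|
| 0.2 | 39.0 | 3.3 to 13.3 | 7.9% to 25.5% |
| 0.4 | 78.0 | 2.5 to 10.0 | 3.1% to 11.4% |
| 0.6 | 117.0 | 1.7 to 6.7 | 1.4% to 5.4% |

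For example, at E = 0.2 and 4 L: 13.3/(39.0 + 13.3) = 25.5%.

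With HCT 0.33, Qb 200–400 mL/min and E 0.2–0.7, the shortfall runs from 0.7% (Qb 400, E 0.7, 1 L) to 33.2% (Qb 200, E 0.2, 4 L).

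**On the Fd scale.** Assume Qb 300, HCT 0.33, E 0.2, 2 L removed, mean Cin 2000 ng/mL over 240 min, and a 150 mg dose. AUC = 480,000 ng·min/mL.

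- SAP formula: 40.2 mL/min × 480,000 = 19.3 mg, Fd = 12.9%.
- With the term: 46.9 mL/min × 480,000 = 22.5 mg, Fd = 15.0%.

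**Hematocrit.** Protocol 4.1 has six port sampling times (0, 0.5, 1, 2, 3 and 4 h), with hematocrit at two of them. The SAP gives no rule for the times between. This can affect the sign of the net error. Fluid removal raises hematocrit, so carrying the 0 h value forward overstates Qp. Suppose 0.33 is carried forward when the true value is 0.35. At E = 0.6 the SAP formula gives 0.6 × 201 = 120.6 mL/min. The correct total is 118.7 with 1 L removed (reported value 1.6% high) and 123.7 with 4 L removed (2.5% low).

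**The 0 h pair.** The Cohort 2 schemas and Protocol 8.5.2 place time 0 before dialysis and before the blood pump starts. There Cin ≈ Cout, so the SAP formula returns about zero. The SAP does not say whether this pair enters the average. If it did, with the other five values equal, the average would be 5/6 of the on-dialysis value. With an ultrafiltration term added indiscriminately, the 0 h pair would instead return about Quf (4.2–16.7 mL/min above), a clearance that does not exist.

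**The case against.** The best reply is that the formula is an explicitly prespecified inlet-plasma-flow estimator and that the error may be small. At extraction 0.6 it is 1–5% on the assumptions above. The sample-size section plans around a 90% CI width of 41.4% of the mean at N = 12 and CV 0.4. That figure was set out for AUC, t1/2 and Cmax, not CLd, and an omitted term does not average out over participants; but the point about size at moderate or high extraction is fair. The sponsor could also define CLd as excluding ultrafiltration. The SAP would then have to say so, and Fd could no longer be described as the whole fraction removed by dialysis.

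A reader might go further in three ways that the documents do not support.

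- That reported CLd must come out low. This holds for the omitted term with other inputs correct. The net sign also depends on how missing hematocrit is filled, which the SAP leaves open.
- That everything needed is already in the database. Pre- and post-dialysis weights are named; ultrafiltration volume and rate are not. They may sit among the unlisted HD details, and the CRF is not available here.
- That the study would wrongly conclude that dialysis removes little drug. SAP 5.1 makes all analyses descriptive with no decision rules, and no threshold for CLd or Fd is given.

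SAP Appendix 2.2 refers to an Analysis and Reporting Plan for endpoint derivations, and text after SAP 6.2.3 is redacted. Either might add detail, but the visible definitions of CLd, Ad and Fd are complete as they stand and contain no such term.

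**Conclusion.** The point holds. The SAP formula leaves out Quf × Cout/Cin, and with other inputs correct it understates CLd, Ad and Fd whenever net fluid is removed. The existence and direction of the omission follow from the SAP's own equations. Its size does not: 1–5% at extraction 0.6 and 8–26% at extraction 0.2 rest wholly on assumed blood flow, hematocrit and fluid volume, and nothing in the documents says which extraction applies to nirmatrelvir. The hematocrit mismatch needs no assumption: the SAP asks for a value at each collection time and the protocol supplies two. Both should be settled before CLd and Fd are calculated.

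**What to change.** Revise SAP 6.2.2 as follows.

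- Use CLd = Qb(1 − HCT) × (Cin − Cout)/Cin + Quf × Cout/Cin at on-dialysis time points only. Exclude the 0 h pre-pump pair from the average CLd.
- Take Quf as a session average: recorded ultrafiltration volume divided by session time if the HD-details CRF captures it, otherwise pre- minus post-dialysis weight (taking 1 kg as 1 L) divided by session time. Session start and end are already needed for the AUC in SAP 6.2.3.
- Interpolate hematocrit linearly between the two measured values.
- Report Fd with the term, and without it as a sensitivity check.

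The cost is one added term, two stated rules and a check of what the CRF records. No new samples or changes to participant care are needed. The downside is that weight change gives only a session average and is also affected by intake and infusions, so recorded ultrafiltration volume is preferable where it exists.
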